### 5.2.5 Conventions for Missing and Incomplete Dates

All dates in the individual subject listings will be presented exactly as recorded on the Electronic Case Report Form (eCRF).

Historical dates, such as the start and stop of concomitant medication and medical history, will not be imputed if missing or incomplete.

Imputation of dates for adverse events with incomplete dates will be performed only for determination of treatment emergence and for the calculation of adverse event duration. Imputed dates will not be presented in data listings. The following algorithm will be used to estimate adverse event start dates for which only partial information is known:

- Completely Missing
  - Earliest of date of first dose of study drug or imputed stop date.
- Missing day and month only
  - If the year is same as the year of first day on drug, then the day and month of the start date of drug will be assigned to the missing fields.
  - If the year is prior to the year of first day on drug, then December 31 will be assigned to the missing fields.
  - If the year is after the year of first day on drug, then January 1 will be assigned to the missing fields.

QMD Ref: Worldwide-TMP-ST-054-1.0_Effective: 12Aug2022	Governing QMD: Worldwide-SOP-ST-026
Confidentiality Statement	
This document is the property of Worldwide Clinical Trials Inc. and may not be duplicated, copied, altered or removed from company without prior approval from Worldwide Quality Assurance or in compliance with Worldwide Standard Operating Procedures.	

Worldwide Clinical Trials Controlled Quality Management Document			
 WORLDWIDE CLINICAL TRIALS	Sponsor:	Flamingo Therapeutics	
	Protocol Number:	FLM-6774-201	
STATISTICAL ANALYSIS PLAN			

- Missing month only
  - Treat day as missing and replace both month and day according to the above procedure.
- Missing day only
  - If the month and year are same as the year and month of first day on drug, then the start date of drug will be assigned to the missing day.
  - If the month and year are before the year and month of first day on drug, then the last day of the month will be assigned to the missing day.
  - If the month and year are after the year and month of first day on drug, then the first day of the month will be assigned to the missing day.

If the AE stop date is complete and the imputed start date as above is after the stop date, the start date will be imputed using the stop date.

Adverse events with partially missing stop dates will be imputed a stop date as follows:

- Year is missing - date left missing.
- Month is missing - impute 'December'.
- Day is missing - impute 'last day of that month'.

## 5.2.6 Conventions for Missing Severity and Causality of Adverse Events

Missing standard toxicity grades will not be imputed. Adverse events with missing toxicity grade will be reported as "No Grade" but will still be included in cumulative summaries for adverse events of any grade.

## 5.2.7 Inexact Values

In the case where a variable (e.g., Safety or Immunogenicity laboratory parameter value) is recorded as "> x", "≥ x", "< x" or "≤ x", a value of x will be applied for analysis purposes.

## 5.2.8 Electrocardiogram (ECG) Data

For ECG data recorded on continuous scales, the mean of the triplicates rounded to the integer will be used for summarization.

## 5.2.9 Vital Signs and Physical Exams

Temperatures reported in Fahrenheit will be reported in Celsius. Height will be reported in centimeters. The following conversations will be used.

$$\text{Celsius} = (\text{Fahrenheit} - 32)/1.8$$

$$\text{Centimeters} = 2.54 \times \text{Inches}$$

QMD Ref: Worldwide-TMP-ST-054-1.0_Effective: 12Aug2022	Governing QMD: Worldwide-SOP-ST-026
Confidentiality Statement	
This document is the property of Worldwide Clinical Trials Inc. and may not be duplicated, copied, altered or removed from company without prior approval from Worldwide Quality Assurance or in compliance with Worldwide Standard Operating Procedures.	

Worldwide Clinical Trials Controlled Quality Management Document		
 WORLDWIDE CLINICAL TRIALS	Sponsor:	Flamingo Therapeutics
	Protocol Number:	FLM-6774-201
STATISTICAL ANALYSIS PLAN		

$$BMI (kg/m^2) = Weight / (Height)^2$$

### 5.2.10 Exposure to Study Drug

A Danvatirsen dose will be considered delayed if it is administered 11 to 14 days after the last dose and skipped if administered 15 to 21 days from the last dose. A second skipped dose will be counted if Danvatirsen is administered 22 to 28 days after the last dose, and so on.

A Pembrolizumab dose will be considered delayed if it is administered 25 to 42 days after the last dose and skipped if administered 43 or more days from the last dose.

Relative Dose Intensity (%) will be calculated separately for Danvatirsen and Pembrolizumab as the actual cumulative dose on study relative to the expected cumulative dose on study, assuming that no doses were missed or reduced. The following formula will be used.

$$\text{Relative Dose Intensity} = \text{Actual Cumulative Dose} / \text{Expected Cumulative Dose} \times 100$$

Actual cumulative dose (mg) for Danvatirsen is calculated as the cumulative sum of Calculated Dose as collected on the CRF during the study. Actual cumulative dose (mg) for Pembrolizumab is calculated as the cumulative sum of Dose as collected on the CRF during the study.

Expected cumulative dose (mg) for Danvatirsen for subjects that have completed at least 1 week of study drug is defined as follows.

$$\text{Expected Cumulative Dose} = (6 + 3 \times \text{Number of Weeks on Study}) * \text{kg}$$

For subjects that discontinued the study before completing 1 week on study, the expected cumulative dose (mg) is 3 mg/kg at day 1, 6 mg/kg at day 3, and 9 mg/kg at day 5.

Expected cumulative dose (mg) for Pembrolizumab is defined as follows.

$$\text{Expected Cumulative Dose (mg)} = 200 \text{ mg} \times \text{Every 3 Weeks on Study}$$

Treatment Duration for Pembrolizumab will be calculated in months as follows.

$$\text{Treatment Duration} = (\text{Date of Last Dose} - \text{Date of First Dose} + 1) / 30.4375$$

Treatment Duration for Danvatirsen will be calculated in months as follows.

$$\text{Treatment Duration} = (\text{Date of Last Dose} - \text{Date of First Dose} + 1) / 30.4375$$

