2 STUDY OBJECTIVES AND ENDPOINTS

Objectives and Endpoints	
Objective	Endpoint
Primary	
To determine the ORR by Response Evaluation Criteria in Solid Tumors version 1.1 (RECIST v1.1) as determined by the Investigator for the combination of danvatirsen and pembrolizumab compared with pembrolizumab alone as first-line treatment of patients with metastatic or unresectable, recurrent HNSCC whose tumors express PD-L1 by CPS ≥ 1	Confirmed ORR (partial response [PR] + CR defined according to RECIST v1.1) (Eisenhauer et al 2009)
Secondary	
To characterize the safety and tolerability of the combination of danvatirsen and pembrolizumab	AEs, serious adverse events (SAEs), physical examinations, clinical laboratory values, and tolerability (dose interruptions/reductions)
To evaluate additional efficacy parameters for the combination of danvatirsen and pembrolizumab compared with pembrolizumab alone	
 • DOR by RECIST v1.1 • Disease control rate (DCR) and CR rate by RECIST v1.1 • ORR and DOR by RECIST v1.1 in tumors with CPS ≥ 20 and ≥ 50 • PFS by RECIST v1.1, defined as the time from randomization to the first documentation of progressive disease (PD) or death from any cause, whichever comes first • OS, defined as time from randomization to death from any cause
To characterize the PK of danvatirsen	PK parameters derived from plasma concentrations of danvatirsen at defined timepoints in the combination regimen
To determine the immunogenicity of danvatirsen	Anti-danvatirsen antibody titers at defined timepoints in the combination regimen
Exploratory	

 • To determine the pharmacodynamic activity of danvatirsen in pre- and on-treatment tumor and blood specimens • To determine the relationship between clinical activity and HPV and other 	
 • STAT3 levels in pre- and on-treatment samples • Gene expression changes (RNA and/or protein) in pre- and on-treatment samples • Determination of HPV positivity

Flamingo Therapeutics
Activity and Safety of Danvatirsen and Pembrolizumab in HNSCC
8 May 2025

Trial ID: FLM-6774-201
Amendment 4

biomarkers in pre- and on-treatment specimens	
---	--

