5 STUDY TREATMENTS AND CONCOMITANT THERAPY

5.1 Study Treatments

Danvatirsen is the investigational medicinal product (IMP). Pembrolizumab is the standard of care. Collectively, these 2 drugs are referred to as the “study treatments” in this protocol. Information on dose and schedule of administration is provided in [Table 1](#).

Table 1: Doses and Schedule of Administration

Study Treatment Name	Danvatirsen	Pembrolizumab
Unit dose strength	Danvatirsen 50 mg/mL	Pembrolizumab 25 mg/mL
Dosage level	3 mg/kg	200 mg fixed dose
Dose formulation	Concentrate for solution for infusion	Concentrate for solution for infusion
Route of administration	IV infusion	IV infusion
IMP	IMP	Standard of care
Sourcing	Sponsor	Study center
Packaging and labeling	IMP will be provided in glass vials. Each vial will be labeled per FDA requirements.	Commercial package

Abbreviations: FDA = Food and Drug Administration; IMP = investigational medicinal product; IV = intravenous

Danvatirsen will be administered via an IV infusion at 3 mg/kg on Days 1, 3, and 5 of Cycle 1 Week 1 with a ± 1 day dosing window and ensuring there is at least 1 day between each danvatirsen dose, i.e. danvatirsen should not be dosed on consecutive days. Note: The visit windows on D1, D3 and D5 do not apply to patients that are participating in the intense PK subset. Danvatirsen is dosed weekly thereafter beginning on Days 8 and 15 of Cycle 1 and on Days 1, 8, and 15 of each subsequent 3-week cycle. Starting at Cycle 1 Week 2, danvatirsen has a ± 2 -day dosing window.

Pembrolizumab will be administered via an IV infusion on Day 1 of each 3-week treatment cycle after all procedures and assessments have been completed. Pembrolizumab has a ± 7 -day dosing window.

On days when both danvatirsen and pembrolizumab are administered, danvatirsen will be administered first. After a window of at least 60 minutes, pembrolizumab will be administered. In the absence of Grade 2 or greater hypersensitivity reactions, the window of time between the two infusions may be reduced to 30 minutes after the first cycle.

Danvatirsen may be held to allow for recovery of toxicities (See [Section 5.4.2](#) for further guidance on dose modifications). Doses missed during the hold will be considered skipped, and the patient should receive their next dose at the scheduled time.

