- f. To facilitate scheduling of predose assessments, a window of -2 days is allowed to obtain the following procedures prior to dosing a patient: physical examination, weight, laboratory safety tests (hematology, serum chemistry, and coagulation), urinalysis, and thyroid function tests.
- g. Vital signs include temperature, pulse, respiratory rate, blood pressure, and oxygen saturation.
- h. For female patients of childbearing potential, serum or urine. The pregnancy test at the 90 day safety follow up visit is required for all patients in the UK and as clinically indicated for all other patients.
- i. Patients are to be followed up for 30 days (+7 days) after the last dose of study treatment for any new reports of AEs, SAEs, and concomitant medications. Tracking of AEs will continue for all patients treated with pembrolizumab for 90 days (±7 days) after the last dose of pembrolizumab or until the initiation of subsequent anticancer therapy.

Flamingo Therapeutics
Activity and Safety of Danvatirsen and Pembrolizumab in HNSCC
8 May 2025

Trial ID: FLM-6774-201
Amendment 4

- j. Tumor assessments performed within 30 days of C1D1 may be used as the baseline tumor assessments. Tumor assessments will be performed every 6 weeks until tumor progression. Patients who discontinue treatment for reasons other than PD will continue to undergo tumor assessments every 6 weeks until PD or the initiation of new anticancer therapy. To facilitate scheduling of tumor assessments, a window of ± 7 days is allowed.
- k. For C1 Week 1, danvatirsen will be administered on D1, D3, and D5 as a loading dose period. Starting with C1 Week 2, danvatirsen will be administered every week on D1, D8, and D15 of each treatment cycle; doses will have a ± 2 -day dosing window.
- l. For pembrolizumab, a window of ± 7 days is allowed for dosing days. Patients will receive pembrolizumab Q3W on D1 of each cycle.
- m. For C1 Week 1, intense PK sampling will be performed on D1 and D5 for 10 US patients in the danvatirsen + pembrolizumab arm. Sparse PK sampling also occurs on C2D1, C5D1 and EOT for all patients in the danvatirsen + pembrolizumab arm. Detailed PK sampling times are provided in [Table 7](#).
- n. ADA will be assessed for danvatirsen + pembrolizumab patients at C1D1, C2D1, C5D1, and EOT, as shown in [Table 8](#).

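### The gap windows in SAP 5.2.10 do not follow the protocol's fixed dosing calendar, so the split between skipped and delayed doses is miscounted

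*SAP*

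**What the plan says.** SAP 5.2.10 sets the following windows, measured from the previous infusion of the same drug.

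- Danvatirsen: a dose is "delayed if it is administered 11 to 14 days after the last dose" and "skipped if administered 15 to 21 days from the last dose". The rule continues: "A second skipped dose will be counted if Danvatirsen is administered 22 to 28 days after the last dose", and so on in steps of 7 days.
- Pembrolizumab: a dose is "delayed if it is administered 25 to 42 days after the last dose" and "skipped if administered 43 or more days from the last dose". No second or later skipped dose is defined.

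SAP 5.11 tabulates the numbers of delayed and skipped doses as separate lines for each drug.

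Protocol 5.1 states the rule for holds once for each drug, in the same words: "Doses missed during the hold will be considered skipped, and the patient should receive their next dose at the scheduled time". Protocol 5.4.1 adds that the cycle structure stays in place during a hold and that skipped doses may result. According to the footnotes in Protocol 8.1, from the second week of Cycle 1 "danvatirsen will be administered every week on D1, D8, and D15 of each treatment cycle", with a dosing window of ±2 days. Pembrolizumab is given on Day 1 of each 21-day cycle, with a dosing window of ±7 days.

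**The concern.** The protocol measures a skipped dose against a calendar that does not move. The SAP measures it by elapsed time since the last infusion, with cut-points that would suit a schedule that shifts when a dose is late. On a fixed calendar, the gap left by one skipped dose (14 or 42 days) is exactly the last day of the SAP's delayed window for each drug. The simplest hold, one dose omitted and the next given on time, is therefore reported as a late dose.

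What is at stake is the reading of the exposure tables. Protocol section 2 names tolerability, described as dose interruptions and reductions, among the secondary endpoints. An omitted dose and a late dose mean different exposure, and SAP 5.11 reports them on separate lines so that they can be told apart.

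**Working it through.** **Inputs.** Interval T = 7 days (danvatirsen, from Cycle 1 Week 2) or 21 days (pembrolizumab); dosing windows ±2 and ±7 days (Protocol 5.1 and 8.1); cut-points from SAP 5.2.10.

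**The SAP rule as a formula.** For a danvatirsen gap G of 15 days or more, the number skipped is ceil(G/7) − 2. This gives 1 for 15–21 days and 2 for 22–28 days, as the SAP states. Below 15 days the count is 0. For pembrolizumab the count is 0 up to 42 days and, as written, 1 from 43 days.

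**Resumption on schedule.** After k skipped doses the gap is G = T(k + 1).

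| Doses skipped (k) | Danvatirsen gap, days | SAP count | Pembrolizumab gap, days | SAP count |
|---|---|---|---|---|
| 1 | 14 | 0 (delayed) | 42 | 0 (delayed) |
| 2 | 21 | 1 | 63 | 1 |
| 3 | 28 | 2 | 84 | 1 |
| 4 | 35 | 3 | 105 | 1 |

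Four separate one-dose danvatirsen holds would appear as 0 skipped and 4 delayed.

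**Doses anywhere in their windows.** With offsets u1 and u2 of the two infusions from their scheduled days, G = T(k + 1) + u2 − u1. There are 5 × 5 = 25 offset pairs for danvatirsen and 15 × 15 = 225 for pembrolizumab. Giving each pair equal weight is an assumption.

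- Danvatirsen, one skip: gaps run from 10 to 18 days. 14 pairs are called delayed, 1 pair (10 days) is called neither, and 10 pairs (15–18 days) are counted correctly. The skip is missed in 15/25 = 60%. For two or three skips the count is also one short in 15/25.
- Pembrolizumab, one skip: gaps run from 28 to 56 days. 120/225 = 53% are called delayed; 105/225 (43–56 days) are counted correctly. For two skips (49–77 days) all 225 pairs are counted as 1.

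**Error in the other direction.** With no skip (k = 0), pembrolizumab gaps run from 7 to 35 days. Those of 25–35 days make up 66/225 = 29% and are flagged as delayed although both infusions are inside the protocol window. For danvatirsen, 1 of 25 pairs (11 days) is flagged. The SAP's lower limits leave a tolerance of 3 days (7 + 3 = 10; 21 + 3 = 24). That matches the ±3-day visit window in the Schedule of Activities, not the dosing windows of ±2 and ±7 days.

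**Loading week.** Scheduled days are 1, 3, 5 and 8. A skipped Day 3 dose leaves 4 days, a skipped Day 5 dose leaves 5 days, and a skipped Day 8 dose leaves 10 days (Day 5 to Day 15). None is counted as either skipped or delayed.

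**Check within SAP 5.2.10.** The expected danvatirsen dose after W weeks is 6 + 3W mg/kg = 3 × (W + 2) mg/kg, which is a fixed calendar of W + 2 doses. At W = 12 that is 42 mg/kg. One skipped dose gives 39/42 = 92.9% relative dose intensity. The same section thus registers a lost dose in one quantity and no skipped dose in the other.

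**The case against.** The windows are coherent for a rolling schedule, in which a dose up to one interval late is a delay and each further week is a skip. Protocol 5.1 and 5.4.3 do speak of pembrolizumab being delayed for toxicity. But Protocol 5.1 goes on to call the doses missed during such a hold skipped, with the next dose at its scheduled time, and 5.4.1 holds the cycles in place. A rolling schedule is not the protocol's.

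Three stronger readings are tempting, and the documents do not support them.

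- *Every hold is undercounted by exactly one.* This is true for danvatirsen when dosing resumes on schedule. Single skips with gaps of 15–18 or 43–56 days are counted correctly. Three pembrolizumab skips are short by two, and that case rests on the SAP's silence about a second skip.
- *The tolerability endpoint is wrong.* No section defines the endpoint as the skipped-dose count. Protocol 9.5 promises doses given, modifications and delays, duration and relative dose intensity. A one-dose hold nearly always still shows, as a delay. Number of doses, dose reductions and the administration listings do not use the windows. Relative dose intensity does not use them either, although SAP 5.11 omits it from its list of summaries.
- *The combination is made to look better tolerated.* The pembrolizumab rule applies to both arms, danvatirsen counts have no comparator, and the false delay flags run the other way. No net direction is shown.

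What remains is that a stated derivation gives wrong skipped and delayed counts under the protocol's own rule.

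**Conclusion.** The point stands as a minor to moderate error in descriptive exposure counts. SAP 5.2.10 disagrees with Protocol 5.1 and 5.4.1, and the two must be reconciled. With on-schedule resumption the undercount is one dose per danvatirsen hold. For pembrolizumab it is one dose for holds of one or two doses and more for longer holds. Within the dosing windows, more than half of single skips are missed for each drug, and about three in ten in-window pembrolizumab intervals are falsely flagged as delayed. Those shares depend on the equal-weight assumption; the on-schedule results do not. The primary ORR analysis and the futility rule are unaffected. The point concerns counting only and takes no view on the dosing or hold rules.

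**What to change.** Replace the gap windows in SAP 5.2.10 with a count based on scheduled slots, for both drugs.

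1. List the scheduled dosing days per patient from the protocol calendar, including Days 1, 3, 5 and 8 of Cycle 1 for danvatirsen.
2. Assign each infusion to its recorded visit or, failing that, its nearest scheduled slot, with one infusion per slot. The recorded visit is needed in the loading week, where slots are only two or three days apart.
3. Count each scheduled slot without an infusion as one skipped dose, with no cap. State where counting stops, for example at the last infusion of that drug.
4. Count a dose as delayed only if it belongs to its slot but was given later than the protocol dosing window.

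A shortcut that rounds the gap divided by 7 or 21 and subtracts 1 should not be used. It gives −1 for each loading-week gap of 2, 2 and 3 days, so a fully compliant patient would total −3. It also misses a skipped Day 8 dose (10/7 rounds to 1, minus 1 = 0). Outside the loading week it is right in 23/25 = 92% of danvatirsen and 205/225 = 91% of pembrolizumab in-window pairs with one skip.

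The cost is one SAP paragraph and one reprogrammed derivation. The administration data are already collected and listed. SAP section 5 requires changes to be approved before database lock, or documented in an addendum afterwards. Section 9 says the final analysis is being brought forward, so this should be settled promptly.

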3.3 Duration of Study Participation

Study participation includes the screening, treatment, and follow-up periods. The screening period is 28 days. After randomization, patients receive treatment in 21-day cycles. The maximum duration of treatment with pembrolizumab is 24 months; there will be no limit of the duration of treatment with danvatirsen.

The follow-up period includes safety follow-up until 30 days (+7 days) after the last dose of study treatment, follow-up for AEs until 90 days (+7 days) after the last dose of pembrolizumab, and survival follow-up every 12 weeks (± 7 days) until death or withdrawal of consent, whichever occurs first. Survival follow-up will continue until at least 15 months after the last patient is randomized in the study.

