9.5 Disposition, Demographic and Baseline Characteristics, and Exposure

The number of patients in each study population and the reasons for exclusion will be summarized.

Patient demographics, baseline characteristics, and exposure will be listed and summarized for the FAS. Patient attributes will be summarized using frequency distributions for categorical variables or descriptive statistics for continuous endpoints, as appropriate.

Descriptive information for danvatirsen and pembrolizumab will be provided regarding the number of doses administered, the number of dose modifications and delays, the duration of treatment, and the relative dose intensity (% of treatment administered compared to targeted).

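### Relative dose intensity is divided by dose expected over an undefined number of weeks on study, not over each drug's own dosing period, so a fully dosed patient can score well below 100%

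*SAP*

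**What the plan says.** In SAP 5.2.10, RDI is derived once per drug and means "the actual cumulative dose on study relative to the expected cumulative dose on study, assuming that no doses were missed or reduced". For danvatirsen, the expected dose is 6 plus 3 times the "Number of Weeks on Study", multiplied by body weight. The expected pembrolizumab dose is 200 mg times "Every 3 Weeks on Study". The danvatirsen formula is "for subjects that have completed at least 1 week of study drug"; for patients who leave before the end of week 1, "the expected cumulative dose (mg) is 3 mg/kg at day 1, 6 mg/kg at day 3, and 9 mg/kg at day 5".

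The same section has a per-drug clock running from first to last dose ("Treatment Duration for Danvatirsen will be calculated in months as follows", with a matching line for pembrolizumab), but the RDI formulas do not use it.

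Protocol 3.3 states: "Study participation includes the screening, treatment, and follow-up periods". Protocol 3.2 counts survival follow-up as part of completing the study. Protocol 9.5 promises a summary of "the relative dose intensity (% of treatment administered compared to targeted" for both drugs. SAP 5.11, which lists the exposure parameters to be summarized, does not include RDI.

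**The concern.** RDI should show how much of the planned treatment was delivered while it was planned. If the denominator keeps growing after a drug has been stopped, RDI partly measures time off that drug. The error then runs in an unhelpful direction: the longer a patient lives after stopping, the lower the apparent delivery.

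Tolerability is a secondary objective, and the combination adds weekly infusions to standard care. A reader of the exposure tables could conclude that the combination was hard to deliver when every planned dose had been given. If the clock is time on any study treatment, pembrolizumab RDI can be lowered this way only in the combination arm, because control patients have no second drug to continue. A comparison of pembrolizumab delivery between arms would then be distorted as well.

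**Working it through.** **Inputs.** Danvatirsen 3 mg/kg three times in week 1 and weekly thereafter; pembrolizumab 200 mg every 3 weeks (Protocol 5.1 and Table 1). Pembrolizumab maximum 24 months/34 cycles, after which danvatirsen may continue alone (Protocol 3.1). One drug may be stopped and the other continued (Protocol 6.1). Treatment and follow-up lengths below are assumptions.

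**1. The plan's own figure.** Full danvatirsen dosing for T weeks gives 3 × (3 + (T − 1)) = 6 + 3T mg/kg. At T = 1 this is 9 mg/kg, which matches the SAP's day 5 value. At T = 24 it is 78 mg/kg, equal to the SAP formula with 24 weeks. So the formula is right if weeks means weeks of danvatirsen treatment.

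**2. Weeks on study including follow-up.** With F weeks of follow-up after T fully dosed weeks:

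- danvatirsen RDI = (6 + 3T) / (6 + 3(T + F))
- pembrolizumab RDI = T / (T + F)

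For T = 24 (8 cycles), with F counted from the end of week 24:

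| Follow-up F | Danvatirsen | Pembrolizumab |
|---|---|---|
| 0 | 78/78 = 100% | 24/24 = 100% |
| 30 days (4.3 weeks) | 78/90.9 = 85.8% | 24/28.3 = 84.8% |
| 90 days (12.9 weeks) | 78/116.6 = 66.9% | 24/36.9 = 65.1% |
| 36 weeks | 78/186 = 41.9% | 24/60 = 40.0% |

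Shorter treatment gives lower values for the same follow-up: with T = 12 and F = 24, the results are 42/114 = 36.8% and 12/36 = 33.3%.

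**3. Weeks on study as time on any study treatment.** Follow-up drops out, but one clock still serves two drugs.

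- All 34 pembrolizumab cycles (34 × 3 = 102 weeks), then danvatirsen alone to week 154: pembrolizumab RDI = 102/154 = 66%, although every planned dose was given.
- Danvatirsen fully dosed for 12 weeks and stopped, pembrolizumab continued to week 36: danvatirsen RDI = (6 + 3 × 12)/(6 + 3 × 36) = 42/114 = 37%.

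**4. Using the SAP's first-to-last-dose duration instead.** After 8 full cycles the last danvatirsen dose falls on day 7 × 21 + 15 = 162 and the last pembrolizumab dose on day 7 × 21 + 1 = 148. Without rounding:

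- danvatirsen: 78 / (6 + 3 × 162/7) = 78/75.4 = 103.4%
- pembrolizumab: 8 / (148/21) = 8/7.05 = 113.5%

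Full dosing then exceeds 100%, because the interval covered by the last dose is cut off. Rounding up to whole weeks (24) or whole cycles (8) gives 78/78 and 8/8, both 100%.

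**The case against.** A reader might infer that the protocol defines weeks on study to include follow-up, and hence that RDI will come out near 40%. The documents do not support either step. Protocol 3.2 and 3.3 describe study completion and study participation; they do not define the term used in the RDI formulas. Protocol 3.3 also includes screening, which a literal reading would have to add too.

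Several passages favor a treatment-period reading:

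- The danvatirsen formula applies after a week of study drug, and the companion rule covers patients who leave before completing a week on study. The two rules cover everyone only if the phrases mean the same thing; otherwise a patient who stops after day 3 and enters survival follow-up fits neither.
- Protocol 5.6 bars other anticancer therapy while on study, yet Protocol 7.6.3 records such therapy during survival follow-up.
- Protocol 9.5 compares treatment given with treatment targeted, and nothing is targeted after discontinuation.

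The size is also uncertain. The 15 months in Protocol 3.3 run from the last randomization and are a study-level minimum, not a length for each patient. Individual follow-up ends at death or withdrawal, and SAP Section 9 reports early termination. Finally, RDI enters no test or go/no-go rule, and SAP 5.11 separately reports doses given, delayed, skipped and reduced.

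All of this stands, and it limits the point to an undefined denominator. It does not remove the problem. The treatment-period reading gives 100% only while both drugs run together, and the protocol expressly allows one to outlast the other.

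**Conclusion.** The denominator is undefined, and neither plausible reading gives a correct RDI for every patient. If follow-up counts, a patient fully dosed for 24 weeks falls to roughly 86%/85%, 67%/65% or 42%/40% (danvatirsen/pembrolizumab) with 30 days, 90 days or 36 weeks of follow-up. These are illustrations over assumed lengths, not forecasts. If only time on any study treatment counts, RDI is wrong for a combination patient who stops one drug before the other, including one who completes the pembrolizumab maximum; the 66% and 37% examples rest on assumed durations.

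The missing entry in SAP 5.11 needs no interpretation: Protocol 9.5 plans the summary, SAP 5.2.10 derives it, and the list omits it. The table shells were not available, so they may already carry it.

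This is a minor point. It touches exposure and tolerability reporting only.

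**What to change.** In SAP 5.2.10, replace time on study with a count specific to each drug:

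- **Danvatirsen:** keep 6 + 3W mg/kg, where the 6 covers the two extra loading doses, and define W as the whole scheduled weeks from the first danvatirsen dose to its discontinuation. Keep the existing rule for week 1.
- **Pembrolizumab:** 200 mg × C, where C is the whole 3-week cycles from the first pembrolizumab dose to its discontinuation or the planned maximum, whichever comes first.
- **Rounding:** count the week or cycle of the last scheduled dose in full, so that full dosing gives exactly 100%. Doses held or skipped before discontinuation remain in the denominator.
- **Patients still on a drug:** end the count at the data cutoff.

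Do not simply substitute the existing first-to-last-dose duration; as shown, it exceeds 100% under full dosing.

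Add RDI to the SAP 5.11 list and confirm that it appears in the exposure tables 14.3.6.1 and 14.3.6.2, which are also interim outputs.

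The cost is a few lines of wording and one derived variable per drug. No new data are collected, since dose dates and discontinuation are already recorded.
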